## Analysis 2:

The second model will adjust for other predictors of cancer detection in order to correct for any imbalances in these between intervention and control group.

First a model will be constructed with known predictors of cancer detection rate. The woman's age and whether she has previously attended screening are known to affect cancer detection rate and so will be included in the model as fixed effects. Then screening centre and batch will be tested for inclusion as levels in the model, using the same process as analysis 1. The treatment will be added to this baseline model.

#### Analysis 3:

This is exploratory follow-up analysis but will not form part of the analysis in the main paper

The third model will be used to determine whether there are particular circumstances in which the intervention is effective.

Predictors to be considered for inclusion will be added separately as fixed effects to the baseline model from analysis 2. Those predictors which improve the model (Wald statistic sig at 10% level) will be added to one model, with those with highest Wald statistic added first. Those for which the Wald statistic remains significant at the 10% level will be retained in the baseline model. Predictors to be considered for inclusion are number of readers involved in arbitration (categorical: 1/2/3 or more), arbitration policy (binary: all recalled cases arbitrated/disagreements only arbitrated), arbitration independence (same/ different readers read and arbitrate the case) whether reader 2 can see reader 1 opinion (categorical: yes on computer/yes but only on paperwork/no), how the mammograms from the previous screening round are displayed (categorical: digital/film pre-hung on a multi-viewer/film available in bag by the workstation), whether the batch was read immediately after another batch(categorical no/yes one reader/yes both readers), the number of cases in the batch, and where in the batch the case was intended to be read (number of cases from beginning/end).

The treatment will be added to this model. The interaction between treatment (intervention or control) and each of these predictors will then be considered for inclusion using the same process and criteria.

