#### Analysis 1:

The first model will include only treatment as a predictor of cancer detection. Levels considered for inclusion in the model will be: case; batch; and centre. To prevent over-fitting, each level will only be included in the final model if it explains a sufficient portion of the variability and improves model fit. Screening centre will be added as a level to the model to account for clustering. It will be retained in the model if it improves model fit (Wald test at the 5% level, see limitations section). Then batch will be considered for addition as a level to this model if it improves model fit according to the same criteria. The treatment will be added to this model.

A sub-analysis of those cases which are intended to be read in the first or last 5 of the batch, younger women  $(\le 52, 53-59, \ge 60)$  and the first batches to be read in a workday (by both readers) will be conducted.

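### Analysis 3 tests centre-level effect modifiers without a random treatment slope, so those interaction tests are too liberal if the treatment effect also varies between centres for other reasons

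*Combined protocol and SAP*

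**What the plan says.** Analysis 3 (SAP section 6) looks for circumstances in which the intervention works. Its candidate terms enter as follows: "Predictors to be considered for inclusion will be added separately as fixed effects to the baseline model from analysis 2". The screening rule is: "Those predictors which improve the model (Wald statistic sig at 10% level) will be added to one model". Treatment is then added, and the interactions follow: "The interaction between treatment (intervention or control) and each of these predictors will then be considered for inclusion using the same process and criteria".

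The random part is inherited. Analysis 1 says: "Screening centre will be added as a level to the model to account for clustering". It keeps centre, and then batch, only if a Wald test at 5% supports it. Analysis 2 says: "Then screening centre and batch will be tested for inclusion as levels in the model, using the same process as analysis 1". Only after that comes the step "The treatment will be added to this baseline model". The levels are therefore settled before treatment is in the model, and no section of the SAP plans a treatment coefficient that varies by centre.

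SAP section 3 (other data collection variables) takes the blinding, arbitration and prior-image items from the survey of centres. The status of the analysis is explicit: "This is exploratory follow-up analysis but will not form part of the analysis in the main paper".

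**The concern.** Batches are randomised within each centre (protocol section 3.4), so every centre supplies its own treatment contrast. Five predictors take a single value per centre: the number of arbitrating readers, the arbitration policy, whether the arbitrators also read the case, whether reader 2 can see reader 1's opinion, and how prior images are shown. An interaction between treatment and one of these asks whether centre-specific effects differ between two or three groups of centres.

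A random intercept for centre absorbs differences in baseline detection rate. It does not absorb differences in treatment effect. If the effect varies between centres for any reason other than the characteristic under test, including another characteristic not yet in the model, that variation is missing from the standard error and the Wald test is too liberal. At stake is the reliability of any centre policy that Analysis 3 singles out as an effect modifier.

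**Working it through.** **Figures in the plan.** The documents give no operating characteristics for the Analysis 3 interactions. The rates used below do reproduce the primary sample size: 7.8 v 8.3 per 1000, two-sided 5%, 80% power and pooled variance give 501,398 per arm, against 501,361 stated in SAP section 2.

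**Inputs.**
- 46 centres (SAP section 3; Supplement 3, section A).
- Women per centre per year: mean 21,921, SD 10,355 (Supplement Table e1).
- Control detection rate 7.8 per 1000; design effect 1.09 as stated (SAP section 2).
- Centre intercept variance 0.058; treatment odds ratio 1.01 (0.96–1.06) (Supplement Table e2).
- Planned effect as a log odds ratio: ln[(0.0083/0.9917)/(0.0078/0.9922)] = 0.063.
- Between-centre SD of the log odds ratio, τ: **not in the documents**. Assumed range 0 to 0.15.

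**Variance of one centre's log odds ratio.** Expected cancers per centre are 21,921 × 0.0078 = 171. With equal arms, v = (4/171) × 1.09 = 0.0255. As a cross-check, the reported interval gives SE = ln(1.06/0.96)/(2 × 1.96) = 0.0253, so v = 46 × 0.0253² = 0.0294. That corresponds to a design effect of about 0.0294/0.0234 = 1.26.

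**Effect of omitting the slope.** The model uses v, but the true variance is v + τ². The ratio of true to model standard error is √(1 + τ²/v), and the actual error of a nominal 10% test is 2[1 − Φ(1.645/√(1 + τ²/v))]. For example, at τ = 0.10 the ratio is √(1 + 0.0100/0.0255) = 1.18 and the error is 2[1 − Φ(1.39)] = 16.3%.

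**Simulation.** The settings were no true interaction, 46 centres with volumes based on Table e1, and a binary characteristic held by half of them. One set (6000 runs) used design effect 1.09, and another (4000 runs) used 1.3, close to what the reported interval implies. The last column re-tests the first set with the between-centre variance estimated and t on 44 degrees of freedom.

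| τ | SE ratio (v = 0.0255) | Formula, v = 0.0255 | Formula, v = 0.0294 | Simulated, DE 1.09 | Simulated, DE 1.3 | With random slope |
|---|---|---|---|---|---|---|
| 0 | 1.00 | 10.0% | 10.0% | 9.6% | 9.7% | 7.7% |
| 0.05 | 1.05 | 11.6% | 11.4% | 12.2% | 12.3% | 9.1% |
| 0.10 | 1.18 | 16.3% | 15.5% | 18.5% | 15.2% | 10.0% |
| 0.15 | 1.37 | 23.1% | 21.6% | 27.6% | 23.0% | 10.1% |

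With the characteristic in a quarter of centres instead of half, the DE 1.09 simulation gives 10.4%, 11.8%, 18.4% and 26.9%, so the result is not sensitive to the split.

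**Predictors that vary within centre.** For a predictor balanced within each centre, the simulated error is 10.8%, 11.1%, 10.5% and 10.1% at τ = 0, 0.10, 0.20 and 0.30. The slope cancels, so reading one batch straight after another, batch size and position in the batch are not materially affected, to the extent that they vary within centres and not between them.

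**Scale of τ.** Relative to the planned 0.063, τ = 0.05 is about 80%, 0.10 is 1.6 times and 0.15 is 2.4 times. At 0.15, 95% of centre odds ratios around 1 would lie between exp(−0.294) = 0.75 and exp(0.294) = 1.34.

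**The case against.** **The random part is inferred.** The SAP never uses the term random intercept, and Analysis 3 does not restate its random terms. The supplement's single intercept variance per level describes models matching Analyses 1 and 2, not Analysis 3. This is fair. But the levels are fixed before treatment enters and nothing later adds a slope, so intercepts only is the natural reading.

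**The heterogeneity needed is large.** Changing reading order alone would have to alter centre odds ratios by more than the whole planned effect before the error rate moves far. This stands, and it limits the point. Some variation is plausible, since Analysis 3 itself supposes that the effect depends on circumstances, and Supplement 3 reports a centre that withdrew over difficulties with the changed order. Nothing in the documents sizes it.

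**The simulation is simpler than the plan.** It takes one binary characteristic, whereas three of the five have three categories, and the plan screens terms separately before combining them. This also stands: the figures describe a single test, not the whole selection procedure. Separately from the slope, five independent tests at 10% already carry a 1 − 0.9⁵ = 41% chance of at least one false positive.

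**Stronger readings that a reader might infer.** One is that recall is worse affected, because events are more frequent. But Analysis 3 sits in the primary-outcome section, SAP section 7 does not clearly extend it to recall, and the supplement's recall table shows only models matching Analyses 1 and 2. Another is that the test treats the woman as the unit. It does not: batch, the randomised unit, is a candidate level and was retained in the reported models. What is missing is only the centre-level treatment slope.

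**Conclusion.** The point holds for the five centre-level predictors in Analysis 3 of cancer detection. In simulation, the actual error of a nominal 10% interaction test is about 10% at τ = 0, 12% at 0.05, 15–19% at 0.10 and 23–28% at 0.15, for one binary characteristic split evenly across 46 centres. This rests on the random-intercept reading of the SAP and on an assumed τ. Inflation is slight unless heterogeneity exceeds the planned log odds ratio of 0.063; above that, centre policies may be named as effect modifiers by chance. The documents do not support saying that they will be.

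This is a minor but cheap improvement. Analysis 3 is exploratory and kept out of the main paper, and the primary and secondary results do not depend on it.

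**What to change.** In Analysis 3, whenever the interaction of treatment with a centre characteristic is tested, add a random treatment slope at centre level, with its covariance with the intercept. Report the slope variance and base the degrees of freedom on the number of centres (about 46 − 2 = 44 for a binary characteristic). An alternative is a random-effects meta-regression of the centre log odds ratios on the characteristic, provided the first stage adjusts for the within-centre predictors. Interactions with predictors that vary within centre can stay as planned.

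The cost is one slope variance and one covariance in an exploratory model, wider intervals for these interactions, and a slightly conservative test if the effect does not vary (7.7% at a nominal 10% in the simulation). A benefit is that the slope variance shows whether the effect differed between centres, which no planned analysis estimates.

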#### 7. Statistical analysis for secondary outcomes

To determine whether the number of disagreements between readers, interval cancer rate, and recall rate is different between the intervention and control groups (secondary aim i, ii, and iii); the same methods will be used as described for the primary analysis above.

The Positive predictive value (PPV) of cancer detection in each study arm will be calculated as the proportion of women recalled who are found to have cancer (secondary aim iii). The difference between PPV in the control and intervention arms will be investigated using the same methods as for the primary outcome, but including only recalled cases.

The effects of the trial introducing the reverse reading order (secondary aim v) will also be analysed. Here, the recall and cancer detection rates for the two reading groups which make up the control arm will be compared. Models will be constructed as for the primary analysis, but using reading order as the predictor of cancer detection rate and recall rate, not trial group membership.

To generate secondary outcome 4 (estimates of cost-effectiveness), the primary outcome from the trial will be used as an input into a health economic model of breast cancer screening. This model will be developed by expanding an earlier breast cancer model by Campbell et al. (2011) and will predict lifetime costs and effects for both intervention and control arms.

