## ii) Secondary

- 1. Recall rate in intervention and control groups
- 2. Referral rate to arbitration, recall rate and cancer detection rate from arbitration, and positive predictive value of arbitration by type of arbitration used. Sensitivity and specificity of arbitration using 3 years follow up data
- 3. Disagreement rate in intervention and control group
- 4. Change in disagreement rate, recall rate, cancer detection rate, and missed cancer rate with intended reading order (and cases since a cancer, recall, and mid-batch break)
- 5. Rate of cancers detected symptomatically in the three years subsequent to screening in intervention and control group. To be collected three years after the trial implementation is complete. This provides a measure of the difference in rates of cancer missed.

iii) Health economicsCost per extra cancer detectedCost per quality adjusted life year gained from the intervention

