#### 2. Power and Sample Size

Currently, 14,700 cancers are detected by screening each year and the cancer detection rate is 7.8 per thousand women screened. (NHS Information Centre, 2012) To detect one extra cancer per 2000 women screened, this would increase the cancer detection rate to around 8.3 cancers per 1000 women screened. To detect this change of 0.5 cancers per 1000 women, for a two-tailed test at 80% power and 5% significance, 501,361 women are required in each arm, see figure 1.

However, as randomisation occurs at the batch level, collected data is clustered and must also be taken into consideration. The sample size of a clustered study must be increased by the Design Effect (DE), which is calculated as  $DE = 1 + (m - 1)\rho$  for a given ICC ( $\rho$ ) and cluster size (m).

ICC was calculated from previous data, using a logistic binomial-Gaussian model (method B) with 1000 Monte Carlo simulations. (Goldstein, 2002) Hence, using the derived ICC of 0.002 and a cluster (batch) size of 40 women, this then gives the DE as 1.09.

Therefore, the overall sample size required is for 1,093,780 women, or 44 breast screening centres for 1 year (On the basis that in England there are 82 centres each screening around 25,000 women per year).

There is no adjustment for drop out or crossover because once the intervention is applied to a screening centre each batch will automatically be randomly assigned to intervention or control groups by the NBSS computer system, and the intervention applied automatically by that same system. A woman could be lost to follow up if she is recalled from screening for further tests and does not attend her follow up appointment, however this is uncommon and so we have assumed low dropout rates for those who are recalled for further tests.

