#### 8. Other analyses with same data set

- Performance with number of cases since the beginning of the batch. [R1intendedOrder]
- Effects on performance of reader completing one session after another and with time of day [Calculate batch in day by assigning a clinic start time for each reader using date and time stamp for first case read for each ReportingSetID].

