#### Models of recall rate by reading order

#### Measures of association

Table e6 shows results of multilevel models for case, batch and centre level factors associated with recall rates in the UK. With all factors controlled for in the multilevel analysis, age of participants and having first ever screen were statistically significantly associated with the odds of recall. Every one year increase in the age of participants increased the odds of recall by 0.4% (OR 1.004; 95% CI 1.003 - 1.006, p<0.001). For participants who have never been screened before the odds of being recalled for re-evaluation were 170% higher than those for participants who have been screened before. When all the factors were controlled for in the final model the odds of a participant being recalled decreases by 0.29% (OR 0.9971; 95% CI 0.9966 – 0.9977, p<0.001) for each case further along in the batch.

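### The SAP specifies no analysis of disagreement or missed cancers by reading order, and its arm contrast for disagreement is nearly insensitive to the hypothesised mechanism

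*Combined protocol and SAP*

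**What the plan says.** Protocol 3.3 keeps two disagreement outcomes apart. Outcome 3 is the disagreement rate by arm. Outcome 4 is "Change in disagreement rate, recall rate, cancer detection rate, and missed cancer rate with intended reading order".

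The SAP deals with position in five places, and none specifies outcome 4 for disagreement or missed cancers:

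- **Section 7, arm comparison.** The stated purpose is "To determine whether the number of disagreements between readers, interval cancer rate, and recall rate is different between the intervention and control groups", using the primary-analysis methods.
- **Section 7, reading-order models.** These compare the two reading groups inside the control arm, and name only recall and cancer detection as outcomes.
- **Section 6, Analysis 1 (carried over to disagreement by section 7).** There is a sub-analysis of cases in the first or last five. Section 3 defines position as the distance from whichever end is nearer, so the scale is folded.
- **Section 6, Analysis 3.** Treatment-by-position interactions are considered, but position is again counted from either end. The model is written for cancer detection, and it is exploratory and kept out of the main paper.
- **Section 8.** It lists "Performance with number of cases since the beginning of the batch", tied to reader 1's intended order. The scale is unfolded, but no outcome and no arm interaction are named.

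Section 7 also uses the label of outcome 4 for something else: "To generate secondary outcome 4 (estimates of cost-effectiveness". The list of dates and decisions in SAP section 1 records nothing about the by-order outcomes.

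Supplement 3 reports disagreement by arm (Table e4). By order it reports only reader 1's detection and recall (Tables e5 and e6).

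**The concern.** The hypothesis in protocol 1.3 is about position: reversing reader 2 should make the two readers' best stretches fall on different cases. Each reader still covers every position in both arms, so each reader's average recall is the same in both. Reversal can shift average disagreement only through the product of the two readers' changes along the batch, which is a second-order quantity.

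The first-order trace is in the slope. If both readers' recall falls along the batch, disagreement should fall with position in the control arm and stay roughly level in the intervention arm. Folding position, as the first-or-last-five sub-analysis does, pools the two ends and cancels that slope.

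At stake is how the reported disagreement result is read (Table e4, adjusted OR 0.997, 95% CI 0.974 to 1.020). A value this close to 1 is expected whether or not reversal separated the readers' peaks, so it says little about the mechanism behind the null primary result.

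**Working it through.** **The plan's own figure.** The SAP states a power calculation only for cancer detection: "for a two-tailed test at 80% power and 5% significance, 501,361 women are required in each arm", where "this would increase the cancer detection rate to around 8.3 cancers per 1000 women screened" from 7.8. Check: (1.96 + 0.8416)² × (0.0078 × 0.9922 + 0.0083 × 0.9917) / 0.0005² = 501,398 per arm, which agrees. Times 2 × 1.09 this is 1,093,048, against 1,093,780 stated. (The SAP says "using the derived ICC of 0.002 and a cluster (batch) size of 40 women, this then gives the DE as 1.09"; 1 + 39 × 0.002 is 1.078, giving 1,081,014. This does not affect the present point.) No power is stated for disagreement.

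**Inputs.**
- Reader 1's recall along the batch: Supplement 3 reports that "the odds of a participant being recalled decreases by 0.29" per cent per case, OR 0.9971 adjusted; 0.9951 unadjusted (Table e6).
- Precision of the arm contrast: Table e4, unadjusted 0.971 to 1.019. SE = ln(1.019/0.971)/3.92 = 0.0123. At 80% power the detectable OR is exp(2.80 × 0.0123) = 1.035.
- Batch length: about 30 (protocol 2.1) or 40 (SAP section 2).
- Assumptions, not in the documents: reader 2's slope; single-reader recall 3.5–6%; disagreement 2.6–4%.

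**Model.** The two recall decisions are correlated latent normals. Thresholds make each reader's recall odds change by the stated OR per case, and the correlation is set to give the assumed disagreement. Control pairs positions (k, k); intervention pairs (k, L + 1 − k). Disagreement at a position is p1 + p2 − 2 × P(both recall).

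**One setting in full.** Recall 5%, disagreement 3%, L = 40, both readers at 0.9971; the correlation needed is 0.93.
- Control disagreement runs from 3.13% at the first case to 2.87% at the last. Intervention disagreement is 3.03% at both ends and 3.00% in the middle.
- Arm contrast: OR 1.0036; z = 0.0036/0.0123 = 0.29; two-sided power 6%.
- Slopes: control −0.0023 log-odds per case, intervention 0. SE of the slope difference = 0.0123/√((40² − 1)/12) = 0.00107; z = 2.15; power 58%. For L = 30 the SE is 0.0123/√((30² − 1)/12) = 0.00142.

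**Range.** Recall/disagreement pairs 3.5/2.6, 4/2.6, 5/3, 5/4 and 6/4%, batches of 30 and 40:

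| Slopes assumed | Arm contrast | Arm × unfolded position |
|---|---|---|
| Both 0.9971 | OR 1.001–1.004, power 5–6% | power 36–61% |
| Both 0.9951 | power about 6–14% | power 77–97% |
| Reader 1 0.9971, reader 2 half that slope | about 5% | 13–20% |
| Reader 1 0.9971, reader 2 flat | 5% | 5% |

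At 0.9971 the first-or-last-five comparison has about 5–7% power. The extreme pairing of 6% recall with 2.6% disagreement raises the arm contrast only to an OR of about 1.007 and power of about 9%, at L = 40.

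**What the interaction measures.** Let a1 and a2 be each reader's contribution to the slope of disagreement. To first order the control slope is a1 + a2 and the intervention slope a1 − a2, so the difference is 2 × a2, which is reader 2's change alone. This is why the power vanishes when reader 2 is flat.

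**The case against.** Several parts of the defence stand.

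- **Disagreement is not analysed solely as one overall rate per arm.** By carrying over the primary-analysis methods, section 7 brings in an adjusted model and the first-or-last-five sub-analysis. The fair criticism is that position is folded there.
- **A reader might infer that the SAP dropped the outcome.** The documents do not show that. The section 8 item could be meant to include disagreement. Section 7 also cites a secondary aim v that protocol 3.2 does not contain, so the SAP follows some other numbering and the reused outcome 4 label proves little. Missing supplement tables show what was reported, not what was planned. Missed cancers also depend on a separate three-year extraction and on follow-on funding (protocol section 7).
- **A reader might infer that the trial reports both readers tiring.** It does not. Tables e5 and e6 concern reader 1 only, and Table e5 shows no fall in detection (OR 0.99987, p = 0.869). Falling recall with level detection is not proof of fatigue. The move from 0.9951 to 0.9971 on adjustment may partly reflect differences between batches. In some centres reader 2 may see reader 1's decision, so equal slopes cannot be presumed.
- **A reader might infer that the arm contrast is an error, or that the interaction would settle the matter.** The contrast answers aim 3 as worded. The interaction depends on reader 2's slope and is not fully powered at 0.9971, so a null would be ambiguous too. Separation of reading order itself can be checked directly, because actual order is collected (protocol 5.4).

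The sizes above also use results that did not exist when the SAP was agreed. That limits any criticism of the authors' foresight, but the second-order argument needs no results.

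**Conclusion.** The point holds as an unspecified analysis with a better method available on data already planned for extraction. It does not show a wrong analysis or a deliberate omission. Two components of protocol outcome 4, disagreement and missed cancers by reading order, have no specified analysis, and none of the SAP's other position items fills the gap. The planned arm contrast for disagreement would detect the mechanism little more often than its 5% false-positive rate if both readers' recall changed at 0.9971 per case. The unfolded interaction does clearly better in that case, and no better than chance if reader 2 does not change along the batch. The sizes rest on the assumed reader 2 slope, recall and disagreement rates, and batch length. The ordering of the two tests held at every setting where reader 2 changes at all. Worth correcting; it does not touch the primary result.

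**What to change.** In SAP section 7 or 8:

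- Name disagreement as a by-position outcome. Specify a multilevel logistic model with arm, reader 1's intended order running from start to end (not folded), batch length and arm × position, with batch and centre levels. Test the interaction two-sided at 5%.
- Report fitted disagreement at the start and end of the batch in each arm, with intervals.
- State that neither a null arm contrast nor a null interaction alone is evidence against the mechanism, since the interaction mainly reflects reader 2's change along the batch.
- Fit the same model to missed cancers if the three-year data are collected.
- Run it after the blinded arm comparison is locked, because SAP section 3 removes the case-order columns for blinding, and label it as a later addition.

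Arm, reader 1's intended order and disagreement are already planned variables, so the cost is SAP wording and one extra model per outcome. The downside is small: another secondary test with modest power.
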